#### Definition of terminology

1. Index date: the date of first oral anticoagulant prescription, namely dabigatran, apixaban, rivaroxaban, edoxaban and warfarin
2. Follow-up period: the day after index date to the earliest of treatment discontinuation, , end of continuous enrolment in the database, end of study period, first occurrence of the event of interest, or death.
3. Any OAC treatment discontinuation: treatment gap of any one of OACs for more than 14 days including the time after switch from one OAC to another OAC (primary analysis)

## **9.3       VARIABLES**

### **9.3.1      Exposures**

Patients prescribed with NOACS (dabigatran, rivaroxaban, apixaban, edoxaban) or warfarin will be grouped as a single exposure group and analysed as a whole. On treatment duration will be expressed in patient year for the follow-up duration to calculate the incidence of various clinical events during the on-treatment duration.

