## Protocol for non-interventional studies based on existing data

Document Number:	c18071759-01
BI Study Number:	1321-0022
BI Investigational Product(s):	Prazaxa (Dabigatran etexilate)
Title:	Medical Need of Non-vitamin K Oral Anti-coagulant Reversal in Japan: Epidemiological Assessment of Emergency Surgery, Major Bleeding due to Trauma and Fracture, using Large Scale Claims Database
Protocol version identifier:	Version 1.0
Date of last version of protocol:	Not Applicable
PASS:	No
EU PAS register number:	Not Applicable
Active substance:	Dabigatran, warfarin, apixaban, rivaroxaban, edoxaban
Medicinal product:	Dabigatran, warfarin, apixaban, rivaroxaban, edoxaban
Product reference:	Not applicable
Procedure number:	Not Applicable
Joint PASS:	No
Research question and objectives:	The primary objective of this study is to assess, for adult patients initiating an oral anticoagulant for non-valvular atrial fibrillation, the incidence rates of emergency surgery, major bleeding due to fracture, and major bleeding due to trauma, overall and stratified by age (<64, 65-74, >75). The secondary objective of the study is to assess the incidence rates of cardiac tamponade or pericardiocentesis, overall and stratified by age (<64, 65-74, >75). .
Country(-ies) of study:	Japan

Author:	
Marketing authorisation holder(s):	
MAH contact person:	
In case of PASS, add: <EU-QPPV:>	Not Applicable
In case of PASS, add: <Signature of EU-QPPV:>	Not Applicable
Date:	18 July 2017

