## 7. RATIONALE AND BACKGROUND

Until 2002 in Japan, administrative claims data were not standardized or coded electronically. There was limited use for Health Authorities policy decision making or in health research (epidemiological, HTA). Ministry of Health, Labor and Welfare launched the Diagnosis Procedure Combination (DPC) system in 2002 linked with the reimbursement system. DPC is a Japanese version of the Diagnosis Related Groups system; such system is implemented in many countries including UK, US and Germany.

MDV provides commercial claims database consisting of medical records from more than 12.94 million in and out-patients (>80% outpatient claims) from 230 large DPC hospitals as of February 2016.

Dabigatran was the first of the non-warfarin oral anti coagulants (NOACs) to be approved and launched in March 2011 in Japan, then three additional NOACs have been launched for an indication of stroke prevention in patients with non-valvular atrial fibrillation (NVAF). Idarucizumab, a specific reversal agent of dabigatran's coagulation effect, has been launched in November of 2016, and is indicated in dabigatran treated patients who undergo emergency operation or experience life threatening bleeding.

Buchelle et al analysed the German claims database system to calculate the incidence of traumatic brain injury in 65 years or older population, and concluded that 4.8 hospital admissions in 1000 patient year of follow-up, and was found to be higher in nursing home resident with higher morbidity and mortality [1]. Curtis et al reported that fracture annual incidence was 155.3 per 10,000 patient-year in men aged 18-24. For age above 90, the incidence was 224.8 per 10,000 patient-year[2].

There has been no epidemiological assessment to investigate the medical need of reversal in patients undergoing emergency surgery or major bleeding from trauma or fracture receiving NOACs in Japan. The objective of this study is to assess the incidence of emergency surgery and major bleeding associated with fracture and head trauma in Japanese patients prescribed with oral anti-coagulants such as warfarin, dabigatran, apixaban, rivaroxaban and edoxaban.

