## 9.5 STUDY SIZE

This study plans no formal hypothesis testing.

The previous study 1160.279 has identified the patients with confirmed 6 months of baseline period and no OAC treatment (defining “treatment naïve” new starter population). The total of these patients was 62,888. The breakdown by OAC initiated was 7,441 for dabigatran, 23,412 for warfarin, 16,026 for apixaban, 12,779 for rivaroxaban and 3,230 for edoxaban. The average on-treatment follow-up period for pooled OAC in patients with at least one year of baseline period prior to index date excluding the time after switching from one OAC to another was approximately 0.3 year. The average on-treatment follow-up period for pooled

OAC including the time after switching with 6 months of baseline period is unknown, but should be longer than 0.3 year.

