## **9.7 DATA ANALYSIS**

### **9.7.1 Main analysis**

#### For the primary outcome

Incidence rate of emergency surgery and major bleeding due to fracture/trauma will be described with each number of patients with event, patient-year and 95% confidence interval overall and stratified by age (age <64, 65-74 and >75). Baseline characteristics of patients overall and stratified by age will be provided in a tabulated format.

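### The title and Section 7 ask about NOAC reversal, but the visible plan reports only a pooled any-OAC rate that includes warfarin starters; add NOAC and warfarin rows, or narrow the title and conclusion

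*Combined protocol and SAP*

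**What the plan says.** The title is "Medical Need of Non-vitamin K Oral Anti-coagulant Reversal in Japan". Section 7 describes the unmet evidence need as emergency surgery or "major bleeding from trauma or fracture receiving NOACs in Japan", and it notes that the one marketed reversal agent it names "is indicated in dabigatran treated patients who undergo emergency operation or experience life threatening bleeding".

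The objectives are broader. The primary objective on the title page concerns "adult patients initiating an oral anticoagulant for non-valvular atrial fibrillation". The abstract and Section 8 also refer to OAC patients generally, and the closing sentence of Section 7 lists warfarin beside the four NOACs.

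Section 9.3.1 follows the objectives: patients on any of the five drugs "will be grouped as a single exposure group and analysed as a whole". Section 9.7.1 gives the primary rates with "patient-year and 95% confidence interval overall and stratified by age (age <64, 65-74 and >75"), and no split by drug or class appears. Section 9.5 does list the starters by drug, as found in study 1160.279: "7,441 for dabigatran, 23,412 for warfarin, 16,026 for apixaban, 12,779 for rivaroxaban and 3,230 for edoxaban".

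**The concern.** Warfarin is a vitamin K antagonist, so warfarin patients fall outside the population named in the title. They are nevertheless the largest single drug group in the sizing cohort. A pooled rate is a weighted mix of the warfarin and NOAC rates, with weights set by who was prescribed what between 2011 and 2016 and for how long. Section 8 describes the population as fairly homogeneous, but the documents do not show that this holds across warfarin and NOAC starters.

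If the two rates differ, a report headed as NOAC reversal need would carry a figure that is not the NOAC rate. A reader could not recover the NOAC rate from the planned tables.

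**Working it through.** **Inputs.** Drug counts come from Section 9.5. Mean on-treatment follow-up of 121 days comes from the abstract (Section 9.5 gives about 0.3 year). That mean is for patients with one year of baseline and, per Section 9.5, excludes time after a switch. The plan says the value for this study is unknown and should be longer, so the patient-years below probably understate what will be available. The documents give no event rate for any drug, so all rates and rate ratios here are assumptions.

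**1. Reproduce the plan's total.** 7,441 + 23,412 + 16,026 + 12,779 + 3,230 = 62,888, which matches the stated total.

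**2. Shares of patients.**
- Warfarin: 23,412/62,888 = 37.2%
- NOACs: 62,888 − 23,412 = 39,476, or 62.8%
- Dabigatran: 7,441/62,888 = 11.8%

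**3. Distance between the pooled and NOAC rates.** Let s be warfarin's share of person-time and R the warfarin:NOAC rate ratio. Then pooled/NOAC = (1 − s) + s × R. With equal mean follow-up by drug, s = 0.372:

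| Assumed R | Pooled/NOAC |
|---|---|
| 0.7 | 0.628 + 0.372 × 0.7 = 0.89 |
| 1.0 | 1.00 |
| 1.3 | 1.11 |
| 1.5 | 1.19 |
| 2.0 | 1.37 |

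Equal follow-up matters. If warfarin follow-up per patient were f times that of NOACs, s = 0.372f/(0.372f + 0.628). This gives 23% at f = 0.5 and 54% at f = 2. The corresponding ranges of pooled/NOAC for R from 0.7 to 2.0 are 0.93 to 1.23 and 0.84 to 1.54.

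**4. Precision of separate rows.** Patient-years = n × 121/365.25. Intervals are exact Poisson, at an assumed 5 events per 1,000 patient-years with event counts rounded.

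| Group | Patient-years | Events | 95% CI per 1,000 |
|---|---|---|---|
| All OAC | 20,834 | 104 | 4.08–6.05 |
| NOACs combined | 13,078 | 65 | 3.84–6.34 |
| Warfarin | 7,756 | 39 | 3.58–6.87 |
| Dabigatran | 2,465 | 12 | 2.52–8.50 |

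At an assumed 1 per 1,000, NOACs combined would have about 13 events (0.53–1.70) and dabigatran about 2 (0.10–2.93). The NOAC row costs little precision overall. The dabigatran row would be sparse, and age strata would thin every row further.

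**The case against.** Pooling is what the written objectives call for. The title page, the abstract, Section 8 and the last sentence of Section 7 all describe any-OAC incidence, and the abstract states the evidence gap in terms of OACs, not NOACs. Section 9.3.1 therefore implements the objective correctly, and the inconsistency could be removed by changing the title alone. This stands, so the point is a mismatch between the stated question and the planned output.

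A reader might go further and infer that the study cannot answer its titled question, or that the pooled rate is a biased estimate. The documents do not support either. The drug started is identifiable, as the Section 9.5 breakdown shows, so the limit lies in the planned tables and not in the data. Bias would presuppose a NOAC-only estimand, which no objective states, and a rate difference on which the documents are silent.

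It is also tempting to say that no NOAC rate is planned at all. The table of contents has blank entries after 9.3.2.2 and after 9.7.1, so outcome or analysis text may have been removed from the public copy. The statement holds for the visible text only, although Section 9.3.1 is intact and states the pooling without exception.

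Finally, the 37.2% counts patients in an earlier study. It describes neither this study's final cohort nor person-time.

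**Conclusion.** The mismatch is real and modest. The planned output meets the any-OAC objective but, in the visible text, gives no rate for the population named in the title and in the Section 7 evidence gap. How far the pooled figure would mislead as a NOAC figure is unknown: not at all if the rates are equal, and −11% to +37% for assumed rate ratios of 0.7 to 2.0 with equal follow-up by drug. Unequal follow-up widens or narrows that range. The case for change does not depend on any particular ratio. It rests on the fact that the planned tables would not let a reader find out. This is a low-cost improvement to reporting; it does not invalidate the planned analysis.

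**What to change.** Keep the pooled OAC rate. In Sections 9.3.1 and 9.7.1, add descriptive rows for NOACs combined and for warfarin, each with patients with event, patient-years and 95% CI, overall and by age where counts allow.

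State how person-time is handled at a switch between warfarin and a NOAC: either assign it to the class being taken, or censor at the switch. The main analysis counts time after a switch without allocating it to a drug. The secondary analysis in Section 9.7.1 already excludes that time, so switches have to be identified in any case.

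A dabigatran row is optional and should be labelled imprecise. Base any conclusion about NOAC reversal on the NOAC row, and state that no between-drug comparison is intended. If the rows are not added, limit the title and conclusion to any-OAC incidence.

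The cost is some extra programming for switches, additional table rows from data already held, wider intervals in the smaller groups, and a risk that readers compare drugs informally despite the disclaimer. Changing only the title and conclusion needs no programming but leaves the NOAC question unanswered.

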### **9.3.2      Outcomes**

#### **9.3.2.1     Primary outcomes**

- Outcome name: A combined endpoint of three outcomes; 1) emergency surgery, (2) major bleeding due to fracture (3) major bleeding due to trauma
- Definition: each events will be defined as following:
  - (1) Emergency Surgery defined as any surgical procedure(International Classification of Diseases (ICD) 10 code K000-879) performed on the same day as hospital admission with additional claims associated with urgent fee MDV codes (114701370, 160000210, 180709110)
  - (2) Major bleeding due to fracture  
Any bleeding associated with hospitalization or blood transfusion (ICD10 code E83.111) accompanied by any fracture (M484, M80, S021, S12, S22, S32, S42, S52, S62, S72, S82, S92, T02, T08, T10, T12, T142) listed as the primary diagnosis requiring most medical resource
  - (3). Major Bleeding due to trauma  
Any bleeding associated with hospitalization or blood transfusion (ICD10 code E83.111) accompanied by any trauma (S00-S09, I620, M125, M164, M165, M172, M173, M191, M483, M872, S065, S066, S081, S089, S130, S18, S230, S480, S481, S532, S533, S580, S581, S589, S633, S634, S680, S681, S684, S688, S689, S780, S789, S889, S980, S981, S982, T050, T053, T058, T059, T116, T136, T147, T794, T795, T796, T797, S271, S272, S330, S334, S382, S480, S481, S532, S580, S581, S589, S633, S634, S680, S681) listed as the primary diagnosis requiring most medical resource

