#### **9.3.2.2     Secondary outcomes**

Outcome name: cardiac tamponade and pericardiocentesis

Event Definition:

- (1). Cardiac tamponade diagnosis (ICD 10 code 4200001) on the same or next day as catheter ablation or PCI (MDV procedure codes 150153910, 150267810, 150263310, 150284310, 150303310, 150345710, 150374910, 150375010, 150375210, 150375310, 150375410)
- (2). Pericardiocentesis (MDV procedure code 140010510) on the same or next day as catheter ablation or PCI (MDV procedure codes as above)

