## 9.9 LIMITATIONS OF THE RESEARCH METHODS

- The sensitivity and specificity of the definitions used in this study, particularly the use of urgent fee, trauma, fracture MDV codes, is unknown. Additionally, there have been no published studies validating the codes to identify emergency surgery, trauma, fracture, cardiac tamponade or pericardiocentesis.
- The findings from this study may not be generalizable to other Japanese population outside of DPC hospitals
- All information of each patient is from consent giving DPC hospitals. If patients have visits to other medical institutions, these data are not included in the MDV data.

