**9.12 BIAS**

- 1. Selection bias: the database is derived from claims arising from DPC hospitals which tend to treat patients with acute and severe disease, and thus may not reflect the general NVAF population of Japan.
- 2. Misclassification bias: outcomes of emergency surgery and bleeding due to fracture/trauma are not validated.

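### Outcome (1) counts an urgent-fee operation only on the day of admission; the rule can only lower the emergency-surgery count, by an unknown amount, and no analysis or stated limitation covers it

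*Combined protocol and SAP*

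**What the plan says.** Section 9.3.2.1 makes emergency surgery the first part of the primary outcome: "A combined endpoint of three outcomes; 1) emergency surgery, (2) major bleeding due to fracture (3) major bleeding due to trauma". The qualifying procedures are broad, "any surgical procedure(International Classification of Diseases (ICD) 10 code K000-879", with no limit by size or bleeding risk. Two further conditions apply together: the operation must be "performed on the same day as hospital admission with additional claims associated with urgent fee MDV codes". The protocol gives no reason for the same-day condition and no route by which urgent surgery later in a stay could count.

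Section 7 sets the clinical context. The reversal agent "is indicated in dabigatran treated patients who undergo emergency operation or experience life threatening bleeding". That description is not tied to the day of admission.

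Section 9.7.1 reports rates that "will be described with each number of patients with event, patient-year and 95% confidence interval overall and stratified by age". It plans no alternative definition of emergency surgery. Section 9.9 says "The sensitivity and specificity of the definitions used in this study, particularly the use of urgent fee, trauma, fracture MDV codes, is unknown", and section 9.12 adds that "outcomes of emergency surgery and bleeding due to fracture/trauma are not validated". Neither mentions the date rule or a direction of error.

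**The concern.** The study describes medical need through an absolute incidence rate. There is no comparator in which an error common to both arms might cancel, so a rule that removes qualifying events passes directly into the reported figure.

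Two kinds of event are removed. One is the patient admitted late in the evening and operated on early the next morning with an urgent fee. The other is the patient admitted for another reason who needs an urgent operation some days into the stay. Both are emergency operations in the sense of section 7, and both fail on the calendar date alone. The report would not show how many there are. A large sample does not help: it narrows the interval around whatever the definition counts.

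**Working it through.** **1. The plan's own size figure.** Section 9.5 gives five treatment groups: 7,441 + 23,412 + 16,026 + 12,779 + 3,230 = 62,888, which matches the stated total. Mean on-treatment follow-up is about 0.3 year in 9.5 and 121 days in the abstract; 121/365.25 = 0.33 year, which agrees. Section 9.5 expects follow-up in this study to be longer, because time after switching is included.

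Patient-years: 62,888 × 0.3 = 18,866; with 121 days, about 20,834.

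**2. Direction of the date rule.** Let the reference be the same definition without the date condition, and let m be the share of reference events dated after the admission day. The same-day count is the reference count × (1 − m). Since m cannot be negative, the count can only stay the same or fall.

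Follow-up ends at the first event (section 9.2), so a missed event also adds some person-time. At 5 per 1,000 and 0.3 year, this is roughly 0.005 × 0.3 / 2 = 0.00075 of the total, which is negligible.

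**3. What a given loss would do.** The documents supply neither the reference rate nor m, so both are assumed here. Intervals are exact Poisson on 18,866 patient-years, with event counts rounded to whole numbers.

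| Reference rate per 1,000 (events) | m | Events counted | Rate per 1,000 | 95% CI | Covers reference? |
|---|---|---|---|---|---|
| 2 (38) | 30% | 27 | 1.43 | 0.94 to 2.08 | yes |
| 2 (38) | 40% | 23 | 1.22 | 0.77 to 1.83 | no |
| 5 (94) | 10% | 85 | 4.51 | 3.60 to 5.57 | yes |
| 5 (94) | 20% | 75 | 3.98 | 3.13 to 4.98 | only just |
| 5 (94) | 30% | 66 | 3.50 | 2.71 to 4.45 | no |
| 10 (189) | 10% | 170 | 9.01 | 7.71 to 10.47 | yes |
| 10 (189) | 20% | 151 | 8.00 | 6.78 to 9.39 | no |

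So a loss of 5% or 10% would sit inside the sampling error at each of these rates, and a loss of 40% would not.

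**4. How m could arise from midnight alone.** If admissions are spread evenly over 24 hours and surgery follows d hours later, the share crossing midnight is d/24: 4/24 = 17%, 6/24 = 25%, 8/24 = 33%, 12/24 = 50%. These figures restate the chosen delay and are not estimates for this study. Urgent operations in existing inpatients come on top.

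**5. Net error against true emergency surgery.** If T is the true number, S the sensitivity and PPV the positive predictive value of the full definition, the observed count is S × T / PPV, so observed/true = S/PPV. With S = 0.8:

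- PPV 1.0: 0.80
- PPV 0.9: 0.89
- PPV 0.8: 1.00
- PPV 0.7: 1.14

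The net error is downward only if S is below PPV. The documents give neither.

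**The case against.** The strongest defence is that the same-day condition protects specificity. Section 9.9 says the accuracy of the urgent-fee codes is unknown, and the protocol does not say whether the fee attaches to the operation, the admission or the visit. If a fee from admission can be linked to a routine operation the next day, the date rule keeps such operations out. Preferring specificity when codes are unvalidated is a legitimate choice. This stands, and it is why the main definition should not be replaced.

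It is also fair that 9.9 and 9.12 already warn that this outcome may be misclassified. The warning is general, however, and says nothing about a rule whose direction is known.

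Four stronger readings are tempting and are not supported:

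- A reader might infer that the primary rate is biased downward overall. Any procedure in a very wide code range qualifies, so false positives could offset or reverse the loss. Some uncounted operations may also enter the combined endpoint through the fracture or trauma bleeding components.
- A reader might take section 9.3.2.2, which accepts events "on the same or next day as catheter ablation or PCI", as a precedent that 9.3.2.1 contradicts. That window attributes a complication to a preceding procedure; the one in 9.3.2.1 identifies urgency. The purposes differ, so there is no inconsistency.
- A reader might expect a larger loss in older patients and hence a distorted age comparison. Nothing in the documents links age to the time from admission to surgery.
- A reader might suppose that every operation after midnight is lost. Admission and surgery both after midnight on one date still count.

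Nor do the documents show whether a patient operated on days into a stay was still receiving the anticoagulant; the 14-day gap rule classifies time, not actual intake.

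**Conclusion.** The point holds as a statement about one condition. The date rule excludes urgent-fee operations on a later calendar day than admission, including those in existing inpatients. Relative to the same definition without it, the emergency-surgery count can only be lower or unchanged. This follows from the wording and needs no assumption.

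Its size cannot be derived from the documents; the tabulated rates and shares are assumptions that show when the loss would exceed sampling error. The net bias in the emergency-surgery rate is unknown, and the effect on the combined endpoint may be smaller than on the surgery component. The gap in the plan is that an absolute rate depends on an unexplained and untested date rule, with no sensitivity analysis and no stated direction. It can be closed cheaply.

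**What to change.** Keep the same-day definition as the main analysis. Then:

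- In 9.7.1, pre-specify a sensitivity analysis that counts urgent-fee surgery on the admission day or the next calendar day, overall and by age group.
- In 9.7.1, add a separate count of urgent-fee operations later in a stay, overall and by age group. The next-day window alone would still miss these.
- In 9.9, state that the same-day rule lowers sensitivity and pushes the emergency-surgery rate downward relative to the same definition without it, and that the net direction is unknown because specificity is unknown.

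The cost is a changed date condition in one extra run, a few table rows and a sentence, all from data already held. The downside is that the wider window may admit some non-urgent next-day operations linked to an urgent fee from admission. Comparison with the same-day result helps to bound this: the number of such operations cannot exceed the number the window adds.

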Data analysis:	Baseline characteristics of patients overall and stratified by age will be provided in a tabulated format.  The main analysis will be on OAC-naïve initiators and will consider outcomes until the complete discontinuation of any OAC (i.e. including the periods during which patients switched from an OAC to another OAC in less than 14 days)		
For the primary objective			

Name of company: Boehringer Ingelheim			
Name of finished medicinal product: Prazaxa			
Name of active ingredient: Dabigatran etexilate			
Protocol date: 18 July 2017	Study number: 1321-0022	Version/Revision: 1.0	Version/Revision date: Not applicable

Incidence rate (overall and age stratified) of emergency surgery, and major bleeding due to fracture, and major bleeding due to trauma will be described with number of patients presenting the event, patient-years and 95% confidence interval overall and stratified by age.
 
For the secondary objective
 
1. Incidence rates (overall and age stratified) of cardiac tamponade or peri-cardiocentesis, along with number of events, patient year of follow-up and 95% confidence interval.
			
Milestones:	
Start of Data Analysis: 1 Aug 2017
 
End of Data Analysis: 19 Sep 2017
 
Study Report: 30 Nov 2017
		

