### **9.3.3 Covariates**

These covariates will be used as patient characteristics for the overall population with the primary outcome events.

1. History of stroke or transient ischemic attack yes/no
2. History of myocardial infarction yes/no
3. History of heart failure yes/no
4. History of diabetes mellitus yes/no
5. History of dyslipidemia
6. History of arterial hypertension yes/no
7. History of peripheral artery disease
8. History of kidney impairment
9. History of valvular disease
10. History of liver disease
11. History of dementia
12. History of trauma
13. History of fracture
14. Nursing home resident
15. History of bleeding
16. Charlson co-morbidity index [3]
17. Concomitant medication yes/no for the following:
  - a. aspirin
  - b. clopidogrel
  - c. angiotensin receptor blockers (ARB) or angiotensin converting enzyme inhibitors (ACE)
  - d. beta-blocker
  - e. amiodarone
  - f. calcium-channel blocker (CCB)
  - g. diuretics
  - h. statins
  - i. proton-pump inhibitor
  - j. H2 receptor antagonist

The disease, Charlson co-morbidity index and concomitant medication are defined as [Table 1-Table 4](#). Nursing home resident is defined as MDV codes 113011710, 113016010, 114020910.

Table 1

Definition of clinical history

Disease	Definition	
	ICD10code	prescription
Stroke or transient ischemic attack	I60-I64, G45	-
Myocardial infarction	I21-I23	-
Heart failure	I110, I130, I132, I420, I50	Prescribed furosemide (defined by generic name)
Diabetes mellitus	E100, E101, E109, E110, E111, E119, E14	Prescribed drugs used in diabetes (defined by Anatomical Therapeutic Chemical (ATC) code as A10)
Dyslipidemia	E78	-
Arterial hypertension	I10-I15	Prescribed 2 or more types of anti-hypertensive (defined in Table 2 )
Peripheral artery disease	I702-I709, I71, I739	-
Kidney impairment	N28	-
Valvular disease	I059, I089, I358, I38, I48	-
Liver disease	K70-K77	-
Dementia	F00-F03, G30	-
Trauma	S00-S09, I620, M125, M164, M165, M172, M173, M191, M483, M872, S065, S066, S081, S089, S130, S18, S230, S480, S481, S532, S533, S580, S581, S589, S633, S634, S680, S681, S684, S688, S689, S780, S789, S889, S980, S981, S982, T050, T053, T058, T059, T116, T136, T147, T794, T795, T796, T797, S271, S272, S330, S334, S382, S480, S481, S532, S580, S581, S589, S633, S634, S680, S681	-
Fracture	M484, M80, S02, S12, S22, S32, S42, S52, S62, S72, S82, S92, T02, T08, T10, T12, T142	-

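### The fracture-bleeding outcome lists only S021 where the otherwise identical Fracture list in Table 1 has all of S02, so the separately reported fracture rate falls short of the outcome's own wording

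*Combined protocol and SAP*

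**What the plan says.** Section 9.3.2.1 sets up the primary outcome as "A combined endpoint of three outcomes; 1) emergency surgery, (2) major bleeding due to fracture (3) major bleeding due to trauma". Component (2) requires the bleeding to be "accompanied by any fracture (M484, M80, S021, S12, S22, S32" and so on, 17 entries in all. Component (3) requires it to be "accompanied by any trauma (S00-S09, I620, M125, M164, M165, M172, M173" and so on through a long list. For both components the fracture or trauma code must be "listed as the primary diagnosis requiring most medical resource".

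Section 9.3.3, Table 1, defines the clinical-history covariates. Its Fracture row reads "M484, M80, S02, S12, S22, S32, S42, S52, S62, S72, S82, S92, T02, T08, T10, T12, T142". Its Trauma row also begins with S00-S09.

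The components are to be reported individually as well as combined. The abstract says that the rates of emergency surgery, "major bleeding due to fracture, and major bleeding due to trauma will be described with number of patients presenting the event", overall and by age. The objectives on the title page and in the abstract likewise name fracture bleeding and trauma bleeding as separate primary rates.

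**The concern.** The outcome claims to take in any fracture, but within S02 it admits one subcode. The protocol itself treats the whole of S02 as fracture when it records fracture history. A patient admitted with a major bleed and, for example, S022 as primary diagnosis has a fracture by Table 1 but no fracture event by the primary outcome.

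At stake is the fracture-bleeding rate, one of the three primary rates, overall and in each age band. If the outcome list is narrower than its label, readers will take the reported rate for something it is not. A smaller consequence is that the History of fracture covariate describes a wider set of codes than the fracture outcome it is tabulated alongside.

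**Working it through.** No power, alpha or sample-size figure bears on this point, and the plan states no figure to reproduce. The check is a comparison of code lists, followed by the algebra of the rate.

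**Step 1: compare the fracture lists.**

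| Source | Entries | S02 entry | Remaining entries |
|---|---|---|---|
| 9.3.2.1, outcome (2) | 17 | S021 | 16 |
| 9.3.3, Table 1, Fracture | 17 | S02 | the same 16 |

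The only codes not common to both lists are S021 and S02. The other nine S-chapter entries (S12, S22, S32, S42, S52, S62, S72, S82, S92) are whole three-character categories in both lists. S021 is the only S-chapter entry cut to a subcode.

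**Step 2: compare the trauma lists.** The lists in 9.3.2.1 (3) and in the Trauma row of Table 1 agree in all 63 entries, including the ten codes repeated at the end (S480 to S681). The outcome and history lists therefore look as if they share a source, which makes an unexplained difference in one fracture entry stand out.

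**Step 3: match the ten possible positions S020 to S029 against each list.**

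| Code | Fracture outcome | Fracture history (Table 1) | Trauma outcome |
|---|---|---|---|
| S021 | yes | yes | yes |
| the other nine | no | yes | yes |

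As primary diagnosis, nine of the ten positions fail outcome (2) and meet outcome (3) through S00-S09. S021 meets both. It is the only fracture-outcome code that also lies in the trauma list.

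**Step 4: effect on the fracture rate.** Let E be the patients with a fracture event as now defined and PY their cohort's patient-years. Let k be the additional patients who would have an event if all of S02 counted. Section 9.2 ends follow-up at the first event of interest, so the wider list also removes some person-time, d, with d at least 0.

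- Rate as written: E / PY
- Rate with S02: (E + k) / (PY − d)
- Ratio of the first to the second: [E / (E + k)] × [(PY − d) / PY], which is at most 1

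The direction is fixed: the rate as written is too low, or equal if k = 0 and d = 0. Ignoring d, the shortfall is the fraction k / (E + k). The documents give neither E nor k, nor any frequency by code, so no number can be attached.

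**Step 5: effect on the combined endpoint.** All of S02 lies within S00-S09, so the union of the fracture and trauma lists is the same with S021 or with S02. The combined count does not change.

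**Step 6: effect of the edit on overlap.** With S02 in outcome (2), all 17 entries match Table 1 and all ten positions count as fracture. All ten still match the trauma list, so the overlap grows from S021 to the whole of S02. The protocol has no rule for a code that sits in both lists.

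**The case against.** Table 1 defines baseline history and is not a second definition of the outcome. The protocol uses differing code sets for related conditions elsewhere: heart failure is I110, I130, I132, I420 and I50 in Table 1, while congestive heart failure for the Charlson score is I110, I130, I132 and I500 in Table 3. A narrower list is therefore not proof of a slip, and the comparison alone does not show which entry is the error. This stands. However, the heart-failure lists carry different labels, whereas the outcome's own label promises any fracture and its list does not deliver that. Either the code or the label must change.

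A reader might infer that the trauma rate is too high by the same events. The documents do not support that. It would follow only if the two components were mutually exclusive, and the protocol states no such rule. Both trauma lists contain S00-S09, and the rationale speaks of fracture and head trauma, so counting S02 events under trauma is a defensible reading. On this the other side is right.

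A reader might also infer that such patients can never count as fracture events. That is too strong. It applies only where the S02 code is the primary diagnosis. A patient whose primary diagnosis is another listed fracture code, such as S12 or T02, still counts.

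Finally, the study is descriptive, with no hypothesis test, and Sections 9.9 and 9.12 already say that the outcome definitions are unvalidated. Section 9.7.1 also writes fracture and trauma bleeding together with a slash, which could be read as a single rate, and a single rate would be unaffected. These points limit the consequence. They do not remove it, because the title page and abstract commit to separate rates and the limitations sections do not mention this mismatch.

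**Conclusion.** The point holds as an inconsistency that affects one primary component rate. Relative to its own wording, outcome (2) omits major bleeds whose primary diagnosis is an S02 code other than S021, and those events appear only under trauma. The fracture rate is understated by about k / (E + k), an amount the documents do not allow to be computed.

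The conclusion rests on three readings of the text: that the outcome is meant to cover any fracture, that a listed three-character category includes its subcodes, and that fracture and trauma bleeding are reported separately. A deliberate restriction to S021 is possible but is nowhere stated. The combined endpoint is unaffected, and nothing shows the trauma rate to be wrong.

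**What to change.** In Section 9.3.2.1 (2), replace S021 with S02, so that the list agrees with Table 1 and with the outcome's label.

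Because all of S02 also lies in the trauma list, add one sentence saying whether S02 events count in both component rates or in one only (for example, with fracture taking precedence). State also that each such event counts once in the combined endpoint.

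If the restriction to S021 was intended, keep the code, stop describing the outcome as any fracture, and give the reason.

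The cost is one code edit and one sentence, with no new data, best done before the outcome programs are written. The downside is that S02 events overlap between the two components unless a precedence rule is applied. Rewriting S00-S09 in the trauma outcome is not needed. If S02 were removed there and not in Table 1, the trauma outcome and trauma history lists, which now agree, would diverge.
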